3.3.2.5 Periodic Contact with Study Subjects

The study site will contact subjects daily during the first 2 weeks of the study, daily during the transition period (ie, while the subject is on both Remodulin and Orenitram), and twice weekly for the first 2 weeks after transitioning (ie, while the subject is on Orenitram and no longer on Remodulin). At all other time points during the study, subjects will be contacted once weekly.

Subjects may be contacted via email in lieu of a telephone call. Email should not replace direct follow-up by telephone or at the study site for clinically meaningful SAEs or other emergent issues. For telephone calls, the subject contact log should be completed and filed to the subject's source documentation. For emails, a copy of the email must be included in the subject's source documentation.

The telephone calls and/or emails after initiation of study drug and up to Week 16 are to be made between the subject and study site personnel to monitor study drug compliance, AEs, PAH symptoms, use of concomitant medications, and to assess dose titration.

In addition to the periodic contact mentioned above performed by the study site, the Investigator may request that nursing support contact the subject through the duration of Remodulin therapy to monitor study drug compliance, AEs, PAH symptoms, use of concomitant medications, and to assess dose titration.

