Transition may be reversed or stopped if the Investigator feels it is necessary due to significant signs or symptoms of PAH or due to serious safety concerns. If the Investigator deems a subject unsuitable for transition to Orenitram due to significant signs or symptoms of PAH or any other serious safety concerns, the subject may remain on Remodulin for the duration of the study. However, the subject should be continually assessed to determine if they become stable enough for transition to Orenitram. All subjects still on Remodulin at Week 8 should transition to Orenitram regardless of their Remodulin dose unless the Investigator deems them unsuitable for transition to Orenitram due to significant signs and symptoms of PAH or any other serious safety concerns.

Following completion of transition, Orenitram dose titration will continue in the outpatient setting through Week 16 to reach the maximum tolerated dose by increasing the dose by 0.125 mg TID every 3 to 4 days as tolerated, with the goal of achieving a maximum tolerated dose by the end of Week 16. A slower titration rate may be used if the subject experiences adverse effects. There is no maximum Orenitram dose during the study.

Orenitram will be dosed TID with food. Dosing will take place approximately every 6 to 8 hours, with adjustments permitted based on the subject's lifestyle and schedule. Study subjects should take their study drug at approximately the same times each day. Tablets must be swallowed whole and not chewed, as this will result in inappropriate delivery of the active ingredient. If the tablet is inadvertently damaged during administration, the subject/caregiver should contact site personnel to be monitored for the onset of symptoms due to possible inappropriate drug release. Subjects must not "make-up" or "double-up" on missed doses of

Orenitram. If dosing is interrupted for longer than 24 hours, consideration should be given to gradually re-titrating the subject's dose to the last dose administered prior to the dose interruption, particularly in cases where the last dose prior to interruption was greater than 3 mg.

In the event of a planned short-term treatment interruption for subjects unable to take oral medications after beginning transition to Orenitram, consider a temporary infusion of SC or IV Remodulin using the following equation to calculate the dose of Remodulin:

Remodulin (ng/kg/min) =
$$(139 \times \text{Orenitram TDD [mg]}) \div \text{weight (kg)}$$

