7.3.4 Transition Visit (Week 2, 4, or 8)

Subjects may transition at Weeks 2, 4, or 8 if they have achieved a minimum Remodulin dose of 20 ng/kg/min and the Investigator deems the subject suitable for transition. Subjects will transition from Remodulin to Orenitram over the course of 1 to 21 days in an inpatient or outpatient setting using a cross-taper method (ie, decreases in Remodulin dose coincide with increases in Orenitram dose). Subjects will be instructed to take the appropriate number of Orenitram tablets based upon their Remodulin dose and the transition schedule chosen by their healthcare provider.

At the discretion of the Investigator, transition may also be reversed or stopped if necessary due to significant signs or symptoms of PAH or due to serious safety concerns. If the Investigator deems a subject unsuitable for transition to Orenitram due to significant signs and symptoms of PAH or any other serious safety concerns, the subject may remain on Remodulin for the duration of the study. However, the subject should be continually assessed to determine if they become stable enough for transition to Orenitram. All subjects still on Remodulin at Week 8 should transition to Orenitram at Week 8 regardless of their Remodulin dose unless the Investigator deems them unsuitable for transition to Orenitram due to significant signs and symptoms of PAH or any other serious safety concerns.

Transition will occur as follows:

- The dose of Remodulin can be reduced no more than 10 ng/kg/min per day for transitions in the outpatient setting. For inpatient transitions, there is no limit on the rate of Remodulin dose reduction.
- The target dose of Orenitram at the end of transition is dependent on the subject's weight and Remodulin dose. Up-titration of Orenitram should coincide with a reduction in the Remodulin dose. The target TDD of Orenitram at the end of

transition will be calculated based upon the following equivalence weight-based formula:

TDD [mg] = 0.0072 * Remodulin dose [ng/kg/min] * weight [kg].

- The Orenitram up-titration dose should be taken at approximately the same time the Remodulin dose is decreased.
- Examples of transition schedules for various subject body weights and Remodulin doses are listed in Appendix I.

The following subject-reported data will be completed by the subject at the Transition Visit prior to all other assessments and prior to initiation of Orenitram: emPHasis-10 questionnaire and TSQM.

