Appendix I. Transition Schedule Examples

3 Days Duration

3 Days Duration for a 70 kg Subject at a Remodulin Dose of 30 ng/kg/min

Transition Day	Remodulin Dose (ng/kg/min)	Orenitram Dose (mg)
	Day 1 (0-24 hours)	22
Morning	30	0
Afternoon	26	0.625
Evening	22	1.375
	Day 2 (24-48 hours)	
Morning	18	2
Afternoon	14	2.625
Evening	10	3.125
	Day 3 (48-72 hours)	
Morning	6	3.75
Afternoon	3	4.375
Evening	0	5

3 Days Duration for a 40 kg Subject at a Remodulin Dose of 30 ng/kg/min

Transition Day	Remodulin Dose (ng/kg/min)	Orenitram Dose (mg)
	Day 1 (0-24 hours)	
Morning	30	0
Afternoon	26	0.375
Evening	22	0.75
	Day 2 (24-48 hours)	
Morning	18	1.125
Afternoon	14	1.5
Evening	10	2
	Day 3 (48-72 hours)	
Morning	6	2.25
Afternoon	3	2.5
Evening	0	2.875

3 Days Duration for a 120 kg Subject at a Remodulin Dose of 30 ng/kg/min

Transition Day	Remodulin Dose (ng/kg/min)	Orenitram Dose (mg)
	Day 1 (0-24 hours)	
Morning	30	0
Afternoon	26	1.125
Evening	22	2.25
	Day 2 (24-48 hours)	
Morning	18	3.5
Afternoon	14	4.625
Evening	10	5.75
	Day 3 (48-72 hours)	
Morning	6	6.875
Afternoon	3	7.75
Evening	0	8.625

3 Days Duration for a 70 kg Subject at a Remodulin Dose of 20 ng/kg/min

Transition Day	Remodulin Dose (ng/kg/min) Day 1 (0-24 hours)	Orenitram Dose (mg)
Morning	20	0
Afternoon	18	0.125
Evening	15	0.25
	Day 2 (24-48 hours)	
Morning	13	0.375
Afternoon	10	0.5
Evening	8	0.625
	Day 3 (48-72 hours)	
Morning	5	0.75
Afternoon	2	0.875
Evening	0	1

3 Days Duration for a 40 kg Subject at a Remodulin Dose of 20 ng/kg/min

Transition Day	Remodulin Dose (ng/kg/min)	Orenitram Dose (mg)
	Day 1 (0-24 hours)	
Morning	20	0
Afternoon	18	0.25
Evening	15	0.5
	Day 2 (24-48 hours)	
Morning	13	0.625
Afternoon	10	1
Evening	8	1.125
	Day 3 (48-72 hours)	
Morning	5	1.5
Afternoon	2	1.75
Evening	0	2

3 Days Duration for a 120 kg Subject at a Remodulin Dose of 20 ng/kg/min

Transition Day	Remodulin Dose (ng/kg/min)	Orenitram Dose (mg)
	Day 1 (0-24 hours)	
Morning	20	0
Afternoon	18	0.625
Evening	15	1.5
	Day 2 (24-48 hours)	
Morning	13	2
Afternoon	10	2.875
Evening	8	3.5
	Day 3 (48-72 hours)	
Morning	5	4.375
Afternoon	2	5.125
Evening	0	5.75

3 Days Duration for a 70 kg Subject at a Remodulin Dose of 40 ng/kg/min

Transition Day	Remodulin Dose (ng/kg/min) Day 1 (0-24 hours)	Orenitram Dose (mg)
Morning	40	0
Afternoon	35	0.875
Evening	30	1.625
	Day 2 (24-48 hours)	
Morning	25	2.5
Afternoon	20	3.375
Evening	15	4.25
	Day 3 (48-72 hours)	
Morning	10	5
Afternoon	5	5.875
Evening	0	6.75

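### Protocol Appendix I: the 3-day schedule for a 70 kg subject at 20 ng/kg/min ends at 1 mg Orenitram per dose, 29.8% of the 3.36 mg set by the Section 7.3.4 formula

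*Protocol*

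**What the plan says.** Protocol Section 7.3.4 states that the target total daily dose (TDD) of Orenitram at the end of "transition will be calculated based upon the following equivalence weight-based formula". The formula is "TDD [mg] = 0.0072 * Remodulin dose [ng/kg/min] * weight [kg"]. The same section adds: "Examples of transition schedules for various subject body weights and Remodulin doses are listed in Appendix I". Section 6.1 has Orenitram taken three times daily, and says that tablets are dispensed according to the Remodulin dose and the schedule the provider selects.

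Appendix I contains 36 tables: four durations (3, 5, 9 and 17 days), three weights (40, 70 and 120 kg) and three Remodulin doses (20, 30 and 40 ng/kg/min). One is headed "3 Days Duration for a 70 kg Subject at a Remodulin Dose of 20 ng/kg/min". Its Remodulin column runs 20, 18, 15, 13, 10, 8, 5, 2, 0. Its Orenitram column runs 0, 0.125, 0.25, 0.375, 0.5, 0.625, 0.75, 0.875, 1 mg.

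Section 6.1 also gives a conversion in the other direction. For planned short interruptions of oral dosing, sites may "consider a temporary infusion of SC or IV Remodulin using the following equation to calculate the dose of Remodulin", namely 139 x TDD / weight.

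**The concern.** The table contradicts the formula it is meant to illustrate. It also contradicts its neighbours: a 40 kg subject on the same 3-day schedule and the same Remodulin dose ends at 2 mg per dose, twice what the 70 kg subject is given.

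The error sits where it could plausibly be used. Apart from the rule that moves remaining subjects at Week 8, 20 ng/kg/min is the lowest Remodulin dose at which transition is allowed, and 70 kg is the weight the protocol uses for its own dose equivalences in Section 1.3. Nothing in the Remodulin column would alert a reader. The daily reductions are 20 to 15, 15 to 8 and 8 to 0 (5, 7 and 8 ng/kg/min), all inside the outpatient limit of 10 ng/kg/min per day in Section 7.3.4. At stake is an unintended fall in treprostinil exposure over 3 days in a patient with PAH.

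**Working it through.** **Inputs.** Formula 0.0072 x Remodulin dose x weight (Section 7.3.4); three doses a day and the inverse equation 139 x TDD / weight (Section 6.1); table entries (Appendix I).

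**Final dose.**
- Formula: 0.0072 x 20 x 70 = 10.08 mg/day; 10.08 / 3 = 3.36 mg per dose.
- Table: 1 mg per dose; 3 x 1 = 3 mg/day.
- Ratio: 1 / 3.36 = 29.8%.

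**The two protocol equations agree with each other.** 139 x 10.08 / 70 = 20.0 ng/kg/min, so the formula is sound. The table's final dose converts to 139 x 3 / 70 = 5.96 ng/kg/min.

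**Other tables.** For the same subject, the 5-day table ends at 3.375 mg and the 9- and 17-day tables at 3.325 mg. Duration does not enter the formula, so all four should agree. The same final-row check on the other 35 tables gives 99.0% (3.325 / 3.36) to 104.2% (2 / 1.92, the 40 kg/20 tables). Only this table fails.

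**Row by row.** Section 7.3.4 states the formula only for the end of transition. Applying it in proportion to the Remodulin withdrawn is an inference: expected dose = 0.0072 x (20 - R) x 70 / 3, where R is the remaining Remodulin dose. The combined equivalent is R + 139 x 3 x dose / 70, treating each entry as if taken three times daily.

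| R | Printed mg | Expected mg | Printed / expected | Combined, printed | Replacement mg | Combined, replacement |
|---|---|---|---|---|---|---|
| 18 | 0.125 | 0.336 | 37.2% | 18.7 | 0.375 | 20.2 |
| 15 | 0.25 | 0.840 | 29.8% | 16.5 | 0.875 | 20.2 |
| 13 | 0.375 | 1.176 | 31.9% | 15.2 | 1.125 | 19.7 |
| 10 | 0.5 | 1.680 | 29.8% | 13.0 | 1.625 | 19.7 |
| 8 | 0.625 | 2.016 | 31.0% | 11.7 | 2 | 19.9 |
| 5 | 0.75 | 2.520 | 29.8% | 9.5 | 2.5 | 19.9 |
| 2 | 0.875 | 3.024 | 28.9% | 7.2 | 3 | 19.9 |
| 0 | 1 | 3.360 | 29.8% | 6.0 | 3.375 | 20.1 |

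Each replacement value is the 0.125 mg multiple nearest the expected dose (largest gap 1.680 - 1.625 = 0.055 mg). All but the last already appear in the 9-day table for the same subject, which has the same Remodulin column.

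**Alternative readings.** If 1 mg were a daily total, the ratio would be 1 / 10.08, about 10%, which is worse. A misread digit cannot produce eight equal steps of 0.125 mg.

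**Smaller irregularities elsewhere.**
- Some entries are not multiples of the smallest tablet, 0.125 mg: 3.325 and 2.85 (repeated), 2.675 and 0.675 (once each). They lie 0.05, 0.025, 0.05 and 0.05 mg from the nearest multiple.
- The 3-, 9- and 17-day 70 kg/30 tables print 3.125, 3.75 and 4.375 mg at Remodulin 10, 6 and 3. The proportional values are 0.168 x 20 = 3.36, 0.168 x 24 = 4.032 and 0.168 x 27 = 4.536 mg (0.168 = 0.0072 x 70 / 3). The shortfalls are 0.235, 0.282 and 0.161 mg. These tables still end at 5 mg against 5.04 mg.

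**The case against.** Appendix I offers examples, and the formula governs. This is one table in 36. To cause harm, a provider would have to match the weight, dose and duration, skip the calculation and overlook the other 70 kg/20 tables. The site contacts subjects "daily during the transition period (ie, while the subject is on both Remodulin and Orenitram"). There is also a way back: "Transition may be reversed or stopped if the Investigator feels it is necessary due to significant signs or symptoms of PAH". The formula is not stated for intermediate steps, and the 70 kg/30 tables show that the appendix does not follow strict proportionality.

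Most of this stands. Harm is conditional, and the row percentages are an inference. None of it bears on the final dose, where the formula does apply and the table fails by 70%.

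Two stronger readings go beyond the documents:
- A reader might infer a long period of under-dosing or a damaged primary endpoint. Titration proceeds by "increasing the dose by 0.125 mg TID every 3 to 4 days as tolerated", so regaining 3.375 mg from 1 mg takes (3.375 - 1) / 0.125 = 19 steps, or 57 to 76 days, and reaching the 4 mg endpoint threshold takes (4 - 1) / 0.125 = 24 steps, or 72 to 96 days. Both figures require that the error goes unnoticed, Remodulin is not resumed and only standard steps are used. Nothing in the documents indicates that any site used this table.
- A reader might infer that Appendix I is generally unreliable. The other 35 tables reach their targets, and their remaining irregularities are small.

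**Conclusion.** The Orenitram column of the 3-day 70 kg/20 ng/kg/min table is wrong. Its final dose is 3 mg/day where the protocol's formula requires 10.08 mg/day. Followed literally, it would reduce treprostinil from 20 to the equivalent of about 6 ng/kg/min in 3 days. The final-dose finding rests only on the stated formula and three-times-daily dosing. The finding that every non-zero entry is low (about 29% to 37% of expected) also assumes proportional replacement at each step. The safeguards lower the chance of harm but do not correct the printed doses. The table should be corrected; the formula, endpoints and statistical analysis are unaffected.

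**What to change.** Replace the Orenitram column of the 3-day 70 kg/20 ng/kg/min table with 0, 0.375, 0.875, 1.125, 1.625, 2, 2.5, 3, 3.375 mg, and notify sites.

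Optionally, proofread the following against the source at the same time; none has a material effect:
- 3.325 mg (final dose of the 9- and 17-day 70 kg/20 tables; 5-day 70 kg/40 at Remodulin 20), probably 3.375.
- 2.85 mg (9- and 17-day 120 kg/20 at Remodulin 10), probably 2.875.
- 2.675 mg (5-day 40 kg/30) and 0.675 mg (5-day 40 kg/20).
- 3.125, 3.75 and 4.375 mg in the 3-, 9- and 17-day 70 kg/30 tables.

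The cost is a short protocol amendment, with the regulatory and IRB/IEC approvals that Sections 12.3 and 13.1 require before implementation, plus the site notice. Data collection and analysis stay as they are.

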Appendix J. REVEAL 2.0 Risk Score

Instructions:

Above is the updated REVEAL 2.0 risk score calculator, which has been modified from the original to refine scoring for several risk variables (Benza 2010; Benza 2018). Subjects with a score of 10 or higher at Screening are ineligible for the study.

- At least 7 of the above 12 variables (with mRAP and PVR considered 2 separate variables within the Right Heart Catheterization) must be used to calculate a valid risk score.
- 3 of the ≥7 variables used for the calculation must include the Screening results for WHO Functional Class, NT-proBNP, and 6-Minute Walk Test.
- Additionally, vital signs (SBP and HR) and SCr (used to calculated eGFR) obtained at screening should be included in the risk score.
- Historical test results may be used to calculate the risk score:
 - A historical echocardiogram may be used if the echocardiogram was performed within 60 days of Screening. A score of +1 will be given for pericardial effusion that is graded as mild, moderate, or severe. A score of 0 will be given for trace pericardial effusion.
 - A historical pulmonary function test may be used if it was performed within 60 days of screening.
 - A historical right heart catheterization (RHC) should be used if it was performed within 180 days of Baseline and the subject has had no changes in their PAH medication regimen (ie, both dosing and drug) since the RHC. If the subject receives an RHC at their Screening visit, the Screening RHC should be used in the subject's REVEAL 2.0 score.

1 INTRODUCTION

The purpose of this Statistical Analysis Plan (SAP) is to provide a description of the statistical methods to be implemented for the analysis of data from the study with protocol number TDE-PH-402. The SAP will be finalized prior to database lock. Any deviations from the SAP after database lock will be documented in the final Clinical Study Report (CSR).

2 STUDY OVERVIEW

2.1 Study Objectives

2.1.1 Primary Objective

The primary objective of the study is to evaluate the dose of Orenitram® (treprostinil) Extended Release Tablets achieved at 16 weeks after induction therapy with Remodulin® (treprostinil) Injection in Pulmonary Arterial Hypertension (PAH) patients.

2.1.2 Secondary Objective

The secondary objective of the study is to assess the effect of treatment with Orenitram (treprostinil) Extended Release tablets at 16 weeks after induction therapy with Remodulin (treprostinil) Injection on clinical response, safety, and tolerability.

2.1.3 Exploratory Objectives

Exploratory objectives of this study are evaluation of pharmacogenomics (genetic/ribonucleic acid [RNA] testing) and evaluation of biomarkers at Baseline, the Transition Visit, and Week 16.

2.2 Study Design

This is a 16-week, multicenter, open-label, uncontrolled study in subjects with PAH.

2.2.1 Overview

The study is a 16-week, open-label, multicenter, uncontrolled study in subjects with PAH.

The following study visits will occur during the 16-week study at the following time points:

- Screening
- Baseline
- Week 2 (Day 15 [±3 days]), Week 4 (Day 29 [±5 days]), Week 8 (Day 57 [±5 days]),
 Week 12 (Day 85 [±5 days]), and Week 16/Early Study Withdrawal (Day 113[±7 days])
- Transition Visit may occur at Weeks 2, 4, or 8 if the subject has achieved a minimum Remodulin dose of 20 ng/kg/min and the Investigator deems the subject suitable for transition. Transition may be reversed or stopped if necessary due to significant signs or symptoms of PAH or due to serious safety concerns.
- Post Transition Visit (7 to 14 days after the Transition Visit)

Table 1 Overall Schedule of Time and Events

	Screening	Baseline ^{a,b}	Treatment Phase						
Study Visit/Week			Week 2s	Week 4s,v	Week 8s	Post Transition Visit ^v	Week 12	Week 16/ Early Study Withdrawal ^c	
Day	-28 to -1	-14 to -1	15 (±3 days)	29 (±5 days)	57 (±5 days)	7 to 14 days after Transition Visit ^v	85 (±5 days)	113 (±7 days)	
Informed consent	X								
Inclusion and exclusion criteria assessment	X	X							
Demographics	X								
PAH history ^d	X								
TSQM ^e		X		X ^s				X	
emPHasis-10 questionnaire		X		X ^s				X	
PAH symptom score		X		X ^s				X	
WHO FC	X	X	X	X	X	X	X	X	
Swan-Ganz right heart catheterization ^f	X								
Medical history	X	X						[
Prior PAH medicationsg	X	X							
Concomitant medicationsgh	X	X	X	X	X	X	X	X	
Physical examinationi	X			X ⁵				X	
Vital signs ^j	X	X	X	X	X	X	X	X	
CD4 count (for subjects with human immunodeficiency virus)	X								

	Screening ^a	Baseline ^{a,b}	Treatment Phase						
Study Visit/Week			Week 2s	Week 4s,v	Week 8s	Post Transition Visit ^v	Week 12 85 (±5 days)	Week 16/ Early Study Withdrawal ^c 113 (±7 days)	
Day			15 (±3 days)	29 (±5 days)	57 (±5 days)	7 to 14 days after Transition Visit ^v			
Clinical laboratory parameters (serum chemistry and hematology)	х	х	Xs					x	
Urine pregnancy test ^k	X	X	X ^s	X	X		X	X	
Echocardiogram		X		X ^s				X	
Serum NT-proBNP ¹	X	X		X*				X	
Blood sample for pharmacogenomics (genetic/RNA) ^m		X							
Blood sample for biomarker evaluation (optional) ^m		х		Xs				х	
6MWT followed by heart-rate recovery (1 minute) and Borg dyspnea score ⁿ	х	х	X°.p	Xop	X ^{o,p}	X^p	X^p	X^p	
Study drug dosing ^q		$X^{r,t}$	$X^{r,t}$	$X^{r,t}$	$X^{r,t}$	$X^{r,t}$	$X^{r,t}$	X ^{r,t}	
Recording of adverse events	X	X	X	X	X	X	X	X	
AE Bothersome Survey		X	X*				X		
Periodic patient contact ^u		X	X	X	X	X	X		
Drug accountability ^w		X	X	X	X	X	X		

6MWD, 6-Minute Walk Distance; 6MWT, 6-Minute Walk Test; ECHO, echocardiogram; eCRF, electronic case report form; FC, Functional Classification; IV, intravenous(ly); NT-proBNP, N-terminal pro-brain natriuretic peptide; PAH, pulmonary arterial hypertension; RHC, right heart catheterization; RNA, ribonucleic acid; SC, subcutaneous(ly); TSQM, Treatment Satisfaction Questionnaire for Medication; WHO, World Health Organization

Screening and Baseline assessments can be conducted up to 28 and 14 days prior to starting the Remodulin infusion, respectively. Screening must occur prior to Baseline assessments to confirm eligibility. Subjects with short-term musculoskeletal conditions (eg. sprained ankle) can be re-screened so that assessments aren't impacted by unusual or extenuating circumstances

- b Following completion of Baseline assessments, subjects will be initiated on Remodulin at 2 ng/kg/min SC or IV in an inpatient or outpatient setting. IV Remodulin may be administered through an indwelling central venous catheter or a peripherally inserted catheter, as clinically indicated. For subjects receiving IV Remodulin through a central venous catheter, it is recommended that the central venous catheter be retained for at least 28 days after the transition from Remodulin.
- The assessments of Week 16/Early Study Withdrawal Visit can occur over 5 days so that assessments can take place on separate days if needed. All assessments should be conducted prior to withdrawing from the study, prior to discontinuation of Orenitram or Remodulin, and as close as possible to the last dose taken by the subject.
- d The subject's PAH diagnosis date, past (noncurrent) PAH medications, PAH etiology, and WHO FC will be recorded.
- These patient-reported outcomes should be completed by subjects prior to other assessments and before imparting news regarding status of their disease. Subjects should be allowed to complete the questionnaires at their own pace, and with minimal help from others.
- f Optional: RHC does not need to be conducted if the patient has an RHC within 180 days of Baseline with a cardiac index ≥2.0 L/min/m² with no changes in PAH medication regimen since the RHC. If an RHC is performed at Screening, values should be obtained for mean right atrial pressure (mRAP) and pulmonary vascular resistance (PVR) to calculate the Screening REVEAL 2.0 risk score.
- g The subject's prior PAH medications and concomitant medications should be recorded on the eCRF.
- The Investigator will record the subject's concomitant medications and record whether the concomitant medication was used to treat an adverse event (including whether prostanoid adverse event or not). For this study, prostanoid adverse events include headache, diarrhea, flushing, nausea, jaw pain, extremity pain, and vomiting.
- A full physical examination is an evaluation of general appearance; mental examination; head, ear, eyes, nose, and throat examinations; and examination of dermatologic, cardiovascular, respiratory, gastrointestinal, musculoskeletal, and neurologic body systems.
- Vital signs include blood pressure, heart rate, respiration rate, height, and weight. Vital signs must be collected after 5 minutes of rest while seated. No other measurements or procedures should occur during the 5 minutes of rest. Vital signs will be collected prior to or at least 30 minutes after the 6MWT.
- k Urine pregnancy tests will be conducted on all female subjects of childbearing potential. A negative urine pregnancy test is required of all female subjects of childbearing potential to be eligible for the study and remain enrolled as a subject.
- Blood samples for NT-proBNP must be drawn prior to conducting the 6MWT and will occur at the Screening Visit, Baseline Visit (prior to Remodulin initiation), the Transition Visit (prior to Orenitram initiation), and the Week 16/Early Study Withdrawal visit.
- Mere local regulations allow, the subject's blood sample will be collected for pharmacogenomic (genetic/RNA) and biomarker analysis for those subjects who consent to the optional testing.
- The subject should rest (seated) for 10 minutes before each 6MWT. If the 6MWT is conducted using supplemental oxygen at Baseline, then all subsequent 6MWTs during the study should be conducted with supplemental oxygen. Similarly, if the Baseline assessment is conducted without supplemental oxygen, then subsequent assessments should also be conducted without oxygen. All efforts should be made to keep the supplemental oxygen flow rate consistent during the 6MWT. The supplemental oxygen flow rate must be recorded at every 6MWT, if applicable. The Borg dyspnea score and heart rate recovery (1 minute) should take place immediately following the 6MWT.
- At the Transition Visit, 6MWT should occur with the subject still on Remodulin therapy, before initiating the transition to Orenitram.
- P When the subject is receiving Orenitram, the 6MWT should occur within 2 to 6 hours of the subject's most recent dose.
- 9 Study drug refers to both Remodulin and Orenitram.
- If the Investigator deems a subject unsuitable for transition to Orenitram due to significant signs and symptoms of PAH or any other serious safety concerns, the subject may remain on Remodulin for the duration of the study. The Investigator may reverse, or stop the transition to Orenitram due to concerns of subject safety.
- In addition to the scheduled assessments, additional testing will be performed at the Transition Visit as indicated. Subjects may transition at Weeks 2, 4, or 8 if they have achieved a minimum Remodulin dose of 20 ng/kg/min and the Investigator deems the subject suitable for transition. Transition may be reversed or stopped for subject safety.
- Subjects should be optimized on Remodulin therapy prior to transition to Orenitram; a dose should be achieved that improves the symptoms of PAH while minimizing excessive pharmacologic effects of Remodulin. Transition from Remodulin to Orenitram will occur over the course of 1 to 21 days.

- ^u The study site will contact subjects daily during the first 2 weeks of the study, daily during the transition period (ie, while the subject is on both Remodulin and Orenitram), and twice weekly for the first 2 weeks after transitioning (ie, while the subject is on Orenitram and no longer on Remodulin). At all other time points during the study, subjects will be contacted once weekly.
- The Post Transition Visit occurs 7 to 14 days after transition from Remodulin to Orenitram is initiated. If the Transition Visit occurs at Week 2, the Week 4 visit can be substituted for the Post Transition Visit (ie. an extra visit is not necessary).
- W Study site or pharmacy personnel should assess drug returned and dosing information to confirm drug accountability.

